## **28) Compensation for Research-Related Injury**

If the subject is injured as a direct result of his or her participation in the study, there will be no compensation provided by the research team. No funds have been set aside. In the unlikely event of injury, subjects or their insurance will be responsible for coverage.

## **29) Economic Burden to Subjects**

Exenatide will be provided for study subjects at no cost. All medical tests, blood tests, and study assessments will also be conducted at no additional cost for each subject. Subjects will otherwise continue to pay for their routine medical care in the usual way.

## **30) Consent Process**

A potential subject who expresses interest in the study will be met by the study coordinator at Biotech One, Suite 100 or Community Healthlink and verify that the patient is interested in participating, understands that participation is voluntary, and understands that declining participation will not affect his or her treatment at the facility.

The PI, Co-Investigator, and study coordinator(s) will clearly explain the study procedure, risks and benefits of participating (including potential risks involving the study medications), and other aspects of the study that are of interest to each subject. Specifically, the study coordinator will review logistical aspects of the study (study timeline, study visit procedures, etc.), while the PI or Co-Investigator will provide information on the study medications. Individuals who express interest will be evaluated by the study coordinator for capacity to provide informed consent. We have developed a questionnaire consisting of approximately 10 true-false questions about important aspects of the study procedures, potential risks, the subject's right to end participation at any time or to speak to a patient advocate, etc. Subjects must score a 100% to participate in the study. Subjects who are judged to be competent will then be asked to sign the study consent form. In addition, prior to starting the study medication, the PI or Co-Investigator will meet with each subject to review the risks of taking the study medication, as well as which medications should be avoided while taking exenatide. In addition, potential participants will also be asked if they would like us to notify their primary care physician or their psychiatrist of their participation in the study.

Many of our potential subjects live in supported living/group home facilities that are staffed with individuals who offer day to day support for these subjects. These staff members are also involved in patient care. As such, we would like to notify a potential subject's supported living/group home staff of the subject's participation in this study. The study team will ask all potential subjects if they live in a supported living/group home facility, and if so, the study team will ask permission to notify the staff at the subject's supported living/group home facility.

We want to enroll a diverse patient population with different levels of cognitive function and varied levels of schizophrenia symptom severity. If the subject lacks the capacity to provide informed consent, then the subject's authorized legal guardian will be present for the consent process. Potential participants and guardians are encouraged to read the consent form and ask questions. After providing a detailed overview of the study, the study coordinator will present the questionnaire consisting of approximately 10 true-false questions about important aspects of the study procedures, potential risks, the subject's right to end participation at any time or to speak to a patient advocate, etc. to the subject and the subject's authorized legal guardian. Participants are further encouraged to solicit input from significant others and/or care providers, if appropriate. To minimize coercion, the consent form has language that clearly spells out that participation in the study is voluntary and refusal to participate will not affect a person's health/mental health care. Subjects and their authorized legal guardians will be required to sign both the informed consent form and the true-false questionnaire form if they agree to participate. We will explain the study in a language understandable to the subject and obtain his or her

assent. Subject will be particularly closely monitored. Subject will be withdrawn if they appear unduly distressed.

The consent process will take place at Community Health Link or at Biotech One, Suite 100. Research personnel will follow HRP-090.

All currently enrolled subjects will be informed of the most recent modification and at their next study visit they will be “re-consented” to the recent changes to the consent form.

### **31) Process to Document Consent in Writing**

Subjects will review the informed consent document with a study coordinator or the PI. Subjects will give their consent by signing the informed consent document. Each subject will receive a paper copy of the signed consent form.

Standard Operating Procedures HRP-090 (Informed Consent Process for Research) and HRP-091 (Written Documentation of Consent) will be followed.

### **32) Drugs or Devices**

Subjects will be given weekly injections of exenatide (2mg per dose) or placebo for 24 weeks as an adjunctive therapy. The medication will be administered by the PI or the co-investigator, or a medically qualified designate such as a registered nurse. The UMass research pharmacy is responsible for randomization and preparation of study medication.

The use of exenatide in this study does not constitute an IND. It is exempt under Section 5 of the Drug Worksheet (HRP-306):

- The drug is lawfully marketed in the United States
- The research is not intended to be reported to the FDA as a well-controlled study in support of a new indication for use nor intended to be used to support any other significant change in the labeling for the drug
- The research is not intended to support a significant change in the advertising for the product
- The research does not involve a route of administration or dosage level or use in a patient population or other factor that significantly increases the risks or decreases the acceptability of the risks associated with the use of the drug product
- The research is conducted in compliance with the marketing limitations described in 21 CFR 312.7).

Please see attached email from the FDA. In addition, the endocrine responses of exenatide treatment are glucose-dependent, which explains the low risk of hypoglycemia with exenatide in both diabetic or non-diabetic patient populations ([Kendall et al., 2005](#), [Aviles-Olmos et al., 2013](#)), as well as healthy volunteers ([Khoo et al., 2010](#)). Therefore the PI feels that it will not affect their acceptability.

Statistical Analysis Plan (SAP)

**The Effect of Adjunctive Exenatide Treatment on Psychopathology, Cognition and Metabolism
in Patients with Schizophrenia**

PI: [name], MPH

Document Date: 11/30/2019

Identifier: NCT02417142

Participants

Adult outpatients with schizophrenia or schizoaffective disorder were recruited from the UMass Memorial Healthcare System in Central Massachusetts. Psychiatric diagnosis was determined using the Structured Clinical Interview for DSM-IV (SCID). Other inclusion criteria included: 1) age 18-65 years; 2) stable dose of the current antipsychotic drug for at least one month; 3) well established compliance with outpatient treatment per treating clinician's judgment; 4) able to complete the cognitive assessment battery (must be English speaking); 5) female subjects will be eligible to participate in the study if they are of non-childbearing potential or of child-bearing potential and willing to practice appropriate birth control methods during the study. Exclusion criteria were: 1) inability to provide informed consent, or for individuals with a legal guardian, inability to provide assent or a lack of informed consent from the legal guardian; 2) current substance abuse; 3) Subjects who are not on a stable dose of an antipsychotic medication for at least a month prior to enrollment; 4) psychiatrically unstable per treating clinician's judgment; 5) Uncontrolled medical condition including uncontrolled hypertension, diabetes, seizure disorder, severe cardiovascular, cerebrovascular, pulmonary, thyroid diseases, and gastroparesis; 6) history of ketoacidosis; 7) currently taking insulin; 8) currently taking meglitinides (repaglinide and nateglinide); 9) currently on immunosuppressant medication regularly including oral steroids; topical and inhalant steroids are allowed; 10) currently on sulfonylurea drugs (e.g. glyburide); 11) current, active chronic infection (including tuberculosis, HIV and hepatitis), malignancy, organ transplantation, blood dyscrasia, central nervous system demyelinating disorder, and any other known autoimmune or inflammatory condition; 12) pregnant or breastfeeding; 13) prisoners; 14) estimated glomerular filtration rate (eGFR) < 35 ml/min. The study was approved by the institutional review board of the University of Massachusetts Medical School and followed the Good Clinical Practice guideline.

Procedures

Baseline visit: Eligible subjects came to the clinic for the baseline visit. Fasting blood samples for glucose, insulin, HbA1c, lipid profile, comprehensive metabolic profile, CBC, high sensitivity C-reactive protein (hsCRP), and tumor necrosis factor α (TNF- α) were obtained. The subject completed the clinical symptoms assessment, the extrapyramidal symptoms (EPS) assessment, and vital signs. Then the subject received the study medication (either exenatide 2mg or placebo weekly injection). The randomization was based on a double-blinded 1:1 ratio using permuted block with randomly varying block size.

Follow-up visits (week 1-24): Subjects came to the clinic weekly to receive the study medication injection; possible side effects were assessed weekly. At week 6, 12, 18, 24 visits, vital signs, the clinical symptoms assessment and the EPS assessment were repeated; fasting blood samples for glucose, insulin, HbA1c, lipid profile, comprehensive metabolic profile, CBC, hsCRP, and TNF- α were obtained.

Clinical symptoms assessment: The clinical symptoms assessment included: The Scale for Assessment of Negative Symptoms (SANS), the Positive and Negative Syndrome Scale (PANSS), the Clinical Global Impression Scale (CGI), the Calgary Depression Scale for Schizophrenia (CDSS), the Heinrichs Carpenter Quality of Life Scale (QLS), the Instrumental

Activities of Daily Living Scale (IADL), and the MATRICS Consensus Cognitive Battery (MCCB).

EPS assessment: The EPS scales included: the Simpson-Angus Scale, the Barnes Akathisia Scale, and the Abnormal Involuntary Movement Scale (AIMS).

Bioassay: Routine blood tests (glucose, insulin, HbA1c, lipid profile, comprehensive metabolic profile, CBC, hsCRP) were performed at the UMass Core Lab. Insulin immunometric assays were performed using an Immulite Analyzer (Diagnostic Product Corporation, Los Angeles, CA) with an intra-assay coefficient of variation of 4.2–7.6%. Fasting plasma glucose was measured with a hexokinase reagent kit (A-gent glucose test, Abbott, South Pasadena, CA). Glucose assays were run in duplicate, and the intra-assay coefficient of variation ranged from 2 to 3%. The homeostatic model assessment of insulin resistance (HOMA-IR) was calculated by the following formula: [fasting serum insulin concentration (μ IU/mL) \times fasting plasma glucose concentration (mmol/L)]/22.5. Hemoglobin A1C (HbA1c) was measured with high performance liquid chromatography using an automated analyzer (normal range 4.5–6.5%) (SmithKline, Van Nuys, CA). Fasting total plasma cholesterol and triglyceride levels were measured enzymatically, and the HDL cholesterol fraction was measured after precipitation of low-density lipoprotein (LDL) and very-low-density lipoprotein (VLDL) with dextran sulfate magnesium. LDL levels were determined by the direct LDL reagents (Roche Diagnostics, Indianapolis, IN). Plasma levels of IL-6 and TNF- α were measured by a commercially available enzyme-linked immunosorbent assay (R&D Systems, Minneapolis, MN, USA). Serum levels of hsCRP were measured via a high-sensitivity latexenhanced immunonephelometric assay on a BN II analyzer.

Statistical analysis: Statistical analysis was performed using SPSS (version 24.0, IBM Corp, Armonk, NY, USA). Descriptive statistics were performed to summarize demographic and clinical characteristics of the study sample. Group comparisons were performed using independent samples t test for continuous variables and the Fisher exact test or Chi-square test for categorical variables. The outcome measures were repeated at different time points. Therefore, analysis of repeated measures using mixed models was performed to compare the change over time in outcome measures between the two treatment groups while controlling for potential confounding variables. The mixed model approach does not require subjects to have the same number of study visits or measurements and uses all available data instead of eliminating subjects with missing data, resulting in unbiased estimates of the model parameters when data are missing at random. Further, for those who completed 24-week treatment, analysis of covariance (ANCOVA) was used to compare change scores from baseline to week 24 between the two treatment groups controlling for potential confounding variables. For all analyses, a P value less than 0.05 (two-tailed) was used for statistical significance.

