### **3) Objectives\***

This is a 24-week, randomized, double-blind, placebo-controlled trial of exenatide weekly injection (2mg per dose) as an adjunctive therapy in 70 schizophrenia subjects to examine exenatide's effects on negative symptoms and cognition.

Primary aim: Examine the efficacy of exenatide weekly injection in improving negative symptoms as measured by the Scale for the Assessment of Negative Symptoms (SANS) total score.

Secondary aims: Examine the efficacy of exenatide in improving cognition as measured by the MATRICS Consensus Cognitive Battery (MCCB) composite score.

Tertiary/exploratory aims:

1. Examine exenatide's effect on schizophrenia symptoms as measured by the Positive and Negative Syndrome Scale (PANSS) total score.
2. Examine the efficacy of exenatide in improving social function as measured by the Instrumental Activities of Daily Living Scale (IADL) and the Heinrichs Carpenter Quality of Life Scale (QLS).
3. Examine exenatide's effect on neuro-protection as measured by the change in hippocampal volume.
4. Examine exenatide's effects on inflammatory markers including serum levels of high sensitivity CRP, IL-6, and TNF- $\alpha$ .
5. Examine the potential moderator role of baseline serum levels of CRP, IL-6, TNF- $\alpha$ , and baseline hippocampal volume for exenatide's effects on negative and cognitive symptoms.
6. Examine the potential mediator role of changes from baseline in serum levels of CRP, IL-6, TNF- $\alpha$ , and hippocampal volume for exenatide's effects on negative and cognitive symptoms.
7. Examine the efficacy of exenatide in reducing body weight and improving glucose metabolism as measured by fasting plasma glucose and HbA1c.
8. Examine the safety and tolerability of exenatide as measured by changes in the side effects questionnaire (SEQ, SEQabbrev), EKG and vital signs

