### Safety Endpoints:

An EKG will be conducted at the beginning and end of the study to assess safety. Vital Signs including blood pressure will be collected at every visit. Data on adverse events will be collected at every visit using the side effects questionnaires (SEQ and SEQabbrev) to assess safety and tolerability.

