## **13) Provisions to Monitor the Data to Ensure the Safety of Subjects\***

The PI and all key personnel involved in this study have completed the Collaborative IRB Training Initiative (CITI), a mandatory tutorial on the responsible conduct of human subject research. The tutorial and institutional policies and procedures governing the conduct of human subjects research are available on the UMass Medical School intranet website and may be accessed by the Investigator and key study personnel if questions arise.

The PI will immediately report to the IRB any unanticipated problems or adverse events that occur during the conduct of the study, after study completion, or after subject withdrawal in accordance with adverse event and unanticipated problems reporting guidelines.

Safety monitoring will have two components. The first will focus on change in psychiatric symptoms. Safety monitoring will also assess the incidence and severity of side effects and the frequency and reason for any medication changes and study medication discontinuation. The PI will discuss likely side effects of exenatide and potential risks of study procedures as part of the informed consent procedure.

Investigators and research personnel who are trained and experienced at conducting assessments in persons with schizophrenia, will assess for deteriorating mental status and/or suicidal ideation. Participants will meet with a study psychiatrist at each visit and have routine monitoring of psychiatric symptoms. The PI will be notified immediately if subject expresses suicidal ideation. The PI is a board certified psychiatrist and has the necessary training and experience to address such events.

The PI can be contacted by phone at all times and the UMass Memorial Emergency Service is available for psychiatric and medical assessment of research subjects. Female patients will be screened for pregnancy during enrollment by a urine pregnancy test.

Any adverse effect reported to study personnel will be reviewed with the PI who will determine whether they are mild, moderate or serious. Potentially serious adverse events will be reviewed by an external monitoring team to determine the likelihood (unlikely/possible/probable) that it is related to the study medication and whether it is safe for the subject to remain in the study.

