#### 2) Acute Pancreatitis.

Based on postmarketing data, exenatide has been associated with acute pancreatitis, including fatal and non-fatal hemorrhagic or necrotizing pancreatitis.

3) Hypoglycemia

The endocrine responses of exenatide treatment are glucose dependent. Exenatide by itself usually does not cause hypoglycemia. Hypoglycemia may occur if it is prescribed with other anti-diabetic medications such as sulfonylurea. Therefore, patients who are currently on sulfonylurea are excluded from the study.

4) Kidney Problems

There have been postmarketing reports of altered renal function with exenatide, including increased serum creatinine, renal impairment, worsened chronic renal failure and acute renal failure, sometimes requiring hemodialysis or kidney transplantation. Some of these events occurred in patients receiving one or more pharmacologic agents known to affect renal function or hydration status such as angiotensin converting enzyme inhibitors, nonsteroidal anti-inflammatory drugs, or diuretics. Some events occurred in patients who had been experiencing nausea, vomiting, or diarrhea, with or without dehydration. Reversibility of altered renal function has been observed in many cases with supportive treatment and discontinuation of potentially causative agents, including exenatide. Exenatide has not been found to be directly nephrotoxic in preclinical or clinical studies.

5) Allergic Reaction

There have been postmarketing reports of serious hypersensitivity reactions (e.g. anaphylaxis and angioedema) in patients treated with exenatide.

6) Common Side effects

The most common side effects of exenatide include nausea, diarrhea, headache, vomiting, constipation, itching at the injection site, small bump at the injection site and indigestion.

Common	Less Common	Rare
Nausea, vomiting, diarrhea, injection site nodule, constipation, headache	dyspepsia	Pain in the stomach area (abdomen)
	Low blood sugar (shakiness, confusion, feeling jittery, weakness, drowsiness and dizziness, hunger,	Shortness of breath, swelling of eyes, face, tongue, lips, throat,

	irritability and fast heartbeat)	arms, hands, feet, ankles or lower legs.  Lump or swelling in the neck, hoarseness, trouble breathing or swallowing,
--	----------------------------------	--

**Risk of EKG testing:** There are also small risks in using EKG equipment, such as skin irritation. However, all research members involved in EKG testing have experience in operating the machinery.

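### The SAP states no by-arm comparison of how many subjects had side effects, how severe these were, or how many subjects stopped because of them, and its change-based analyses do not supply one

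*SAP*

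**What the plan says.** Aim 8 in Protocol section 3 (tertiary/exploratory) is: "Examine the safety and tolerability of exenatide as measured by changes in the side effects questionnaire (SEQ, SEQabbrev), EKG and vital signs". Section 9, under Safety Endpoints, makes the questionnaires the adverse-event tool: "Data on adverse events will be collected at every visit using the side effects questionnaires (SEQ and SEQabbrev"). The SAP, under Procedures, confirms for weeks 1 to 24 that "possible side effects were assessed weekly".

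The SAP's Statistical analysis section gives two analyses for repeated outcomes. The first is the mixed model: "analysis of repeated measures using mixed models was performed to compare the change over time in outcome measures between the two treatment groups". It is described as an approach that "uses all available data instead of eliminating subjects with missing data". The second is an ANCOVA of change from baseline to week 24, restricted to subjects who completed 24 weeks of treatment. The section also names Fisher's exact and chi-square tests for categorical variables, without saying which variables. It does not mention the side-effects questionnaires, adverse events, severity, discontinuation or a safety population.

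Incidence appears in Protocol section 13, as monitoring: "Safety monitoring will also assess the incidence and severity of side effects". The same sentence covers reasons for stopping study medication, and the section provides for annual DSMB review. Section 14 adds a side-effect assessment at an exit visit for withdrawn subjects. Section 15 lists the expected effects ("The most common side effects of exenatide include nausea, diarrhea, headache, vomiting, constipation" and others) without rates, onset or duration.

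**The concern.** For side effects such as nausea or vomiting, a reader wants to know how many subjects had the effect, how severe it was, and how many gave up the drug because of it. A change score answers none of these. In a baseline-to-week-24 comparison of completers, a subject whose nausea came and went contributes no change, and a subject who stopped because of it is not in the analysis at all. The exit-visit assessment, which would record the second subject, has no stated use.

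Up to 24 weekly side-effect assessments per subject would then be collected with no stated end-of-trial estimate of the quantity they are best suited to give. Tolerability is an exploratory aim, but it is the trial's stated measure of harm.

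**Working it through.** **1. The plan's own figure.** The only statistical figure is in Protocol section 12: 60 evaluable subjects, effect size 0.74, two-sided 0.05, 80% power. With 30 per arm the noncentrality is 0.74 × √(30/2) = 2.87 on 58 degrees of freedom, and power is 80.5%. It reproduces, but it concerns efficacy. No figure is given for tolerability.

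**2. What each stated element can answer.**

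| Element | Subjects included | How many affected? | How severe? | How many stopped? |
|---|---|---|---|---|
| Mixed model (SAP) | all available data | no, mean course only | mean only | no |
| Week-24 ANCOVA (SAP) | completers | no | week 24 only | no, they are excluded |
| Fisher / chi-square (SAP) | not assigned to any safety variable | possible, not stated | possible, not stated | possible, not stated |
| Monitoring (Protocol 13) | all, during the trial | yes, but no by-arm analysis stated | same | same |

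**3. Size of the gap: inputs.** From the documents: 70 randomised 1:1, so 35 per arm, and 24 weekly assessments. Assumed, because the documents give nothing: effects start in weeks 1-8 and last 4 visits; 30% of affected subjects stop; unaffected subjects report the symptom at 3% of visits; true ever-rates are 30% v 5%, 40% v 10% or 50% v 10%.

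**4. Completer week-24 contrast.** Onset by week 8 plus four visits means every effect has ended by about week 12, so week 24 shows background only. The simulated difference is 0.001, 0.000 and 0.000 in the three cases, with p<0.05 in about 1% of trials. A second set of assumptions (onset in weeks 1-4, lasting 1-4 weeks, 30%, 40% or 50% v 10%) gives p<0.05 in 4-7%, about the false-positive rate.

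**5. Per-subject comparison.** The expected observed rate is p + (1 − p) × b, where b is the chance that an unaffected subject is counted through background alone.

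- Any visit: b = 1 − 0.97^24 = 0.52.
- Two consecutive visits: b is at most 23 × 0.03² = 0.021, so about 0.02.

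| True ever-rates | Two-visit rule: observed | Fisher power | Any-visit rule: observed | Fisher power |
|---|---|---|---|---|
| 30% v 5% | 31% v 7% | about 70% | 66% v 54% | about 13% |
| 40% v 10% | 41% v 12% | about 75% | 71% v 57% | about 19% |
| 50% v 10% | 51% v 12% | about 94% | 76% v 57% | about 33% |

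Repeat simulations agree within about 2 percentage points. The counting rule therefore matters as much as the move to per-subject counts. If ascertainment were perfect, with no background reports, exact Fisher power for 30%, 40% and 50% v 10% would be 46%, 78% and 95%.

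**6. Mixed model.** Under the second set of assumptions, a contrast of weeks 1-4 with baseline is significant in about 34-37%, 63-66% and 82-83% of runs. A linear slope difference is significant in 38%, 72% and 89% if nobody stops, and in 20%, 34% and 60% if half of affected subjects stop. Its mean is negative throughout: an early effect that resolves appears as side effects falling on exenatide. The SAP does not say whether time is categorical or linear.

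**7. Precision.** For 41% v 12%, the standard error is √(0.41 × 0.59/35 + 0.12 × 0.88/35) = 0.10, so the 95% interval is about ±20 percentage points.

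**The case against.** Four arguments have force.

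- **The SAP never says that the questionnaires enter these models.** The reading comes from aim 8's use of change plus the SAP's generic reference to outcome measures. Protocol section 12 states its mixed model for clinical symptoms and cognition only. This stands. If the questionnaires are outside the models, their analysis is simply unspecified, and the same fix is needed.
- **The mixed model uses all available data.** Subjects who stop contribute until they leave, and a model with visit as a category can show early differences (step 6). A reader might infer that every planned analysis would report no difference in tolerability. The documents do not support that. It holds for the completer analysis, and only for effects that have resolved or led to stopping.
- **Incidence is covered elsewhere.** Section 13 assesses incidence, severity and reasons for discontinuation, the DSMB reviews adverse events annually, and the SAP names Fisher's test. Routine adverse-event tables may well be intended. But monitoring during the trial is not a stated end-of-trial comparison, and the tests are not assigned to adverse events.
- **Timing is not in the documents.** Section 15 gives no onset or duration, and injections continue weekly, so some effects could recur up to week 24. This stands: the near-zero week-24 difference in step 4 is built in by the assumption that effects are early and short, and it shrinks as a concern if they persist.

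**Conclusion.** The gap is real but limited. The plan collects side effects weekly, defines tolerability by change, and states no by-arm comparison of incidence, severity or discontinuation. If the questionnaires are analysed as outcome measures, the completer ANCOVA cannot show effects that resolved or led to stopping, and the mixed model, whatever it detects, estimates a different quantity.

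The power figures rest wholly on assumed rates, timing and background. They show that a per-subject comparison can be informative at 35 per arm when background reports are filtered (about 70-94%), and much less so when any single report counts (about 13-33%). They do not show that the trial's safety conclusion would be wrong. The change should be made, but it bears on an exploratory aim and leaves the efficacy analysis untouched.

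**What to change.** In the SAP, state the tolerability analysis as a per-subject comparison by arm:

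- **Population and data:** everyone who received at least one injection, using all weekly SEQ/SEQabbrev and exit-visit data. Say which form is used at which visit and which assessment is the baseline; section 10 does not list the questionnaires at the baseline visit, although section 9 implies them.
- **Count:** for each side effect, the number and percentage of subjects in whom it was new or worse than baseline. Apply a pre-stated rule that limits background noise, for example present at two consecutive visits or above a stated severity, and show the any-visit count alongside. Under a two-visit rule, an effect that ends in stopping after one report would be missed; the any-visit and discontinuation counts cover that case.
- **Also by arm:** worst severity, and the number stopping study drug for an adverse event.
- **Reporting:** risk differences with 95% CIs. Treat Fisher p-values as descriptive, since several effects are tabulated, and say that non-significance at about 35 per arm is not evidence of no harm.
- **Aim 8:** reword to incidence and severity of side effects, and changes in EKG and vital signs. Keep change analyses for those two.

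The cost is SAP wording and standard tables from data already collected. No dose, visit or stopping rule changes. The SAP is written in the past tense; if treatment codes have been opened, label this as an addendum.
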